### **11.7 Baseline Demographic Characteristics**

Demographic data including, but not limited to, age, race, sex and ethnicity and baseline characteristics including, but not limited to, DCNVA, UCNVA, UCDVA, BCDVA, manifest refraction spherical equivalent (MRSE), cycloplegic refraction spherical equivalent (CRSE), will be reported for each subject. Baseline characteristics such as age, sex, race, and near visual acuity will be summarized.

### **11.8 Analysis of Effectiveness Data**

As noted previously, both Objective #1 and Objective #2 of the primary effectiveness endpoint must be satisfied in order for the study to be considered a success.

#### **Analysis of Objective #1:**

The one-sided 97.5% lower confidence limit of the 12-month responder rate will be calculated based on the exact binomial distribution. This goal is met if the one-sided 97.5% lower confidence limit of the 12-month responder rate is at least 75%.

The percentage of primary eyes achieving the Effectiveness Endpoint at 12 months will be compared among the study sites. The Fisher's exact test will be used to evaluate the possible study site effect. If the site effect is significant, i.e.,  $p\text{-value} \leq 0.15$ , then 12-month responder rates stratified by study site will be provided and the average of the site 12-month responder rates will be calculated. The normal distribution approximation will be used to estimate the one-sided lower 97.5% confidence limit for the average 12-month responder rate.

Fisher's exact test will also be used to assess the effects of subject sex, race and age category at surgery on the 12-month responder rates for primary eyes using a p-value of 0.15. For this analysis, age will be categorized into 3 interval groups (i.e., 45-49, 50-54, and 55-60).

#### **Analysis of Objective #2:**

The number and percentage of primary eyes achieving the Effectiveness Endpoint at 6 months will be summarized for the randomized surgery group and randomized control group separately. The two-sided Fisher's exact test will be used to compare the difference between 6-month responder rates of the two randomized groups.

In order to assess potential differences of randomized group allocation and/or site 6-month responder rates, a logistic regression analysis examining with the following will be performed:

- treatment effect (the randomized surgery group and the randomized control group at that same site),
- study site effect (site by site success rate comparison), and
- site by treatment interaction

If there is a significant difference ( $p \leq 0.15$ ) in treatment effect, study site effect, or a significant interaction effect between study site effect and treatment effect ( $p \leq 0.15$ ), then the 6-month responder rate for each study group and the difference in the 6-month responder rate between the two randomized groups ( $p_{\text{treatment}} - p_{\text{deferred}}$ ) will be summarized by each study site.

### **Sensitivity Analysis of Objective #1:**

Sensitivity analysis will be performed for Objective #1 using the following imputation methods for missing 12-month data:

- **Best Case Analysis:** All discontinued primary eyes will be imputed as effectiveness failures. For primary eyes lost to follow-up or for primary eyes missing 12-month visit data, the best value from any protocol scheduled visit at 1 month or later (1 month, 3 month or 6 month visit) will be used. If such visit data does not exist for a primary eye, the effectiveness will be imputed as a success.
- **Worst Case Analysis:** All discontinued primary eyes will be imputed as effectiveness failures. For primary eyes lost to follow-up or missing 12 month visit data, the worst value from any protocol scheduled visit at 1 month or later (1 month, 3 month or 6 month visit) will be used. If such visit data does not exist for a primary eye, the effectiveness will be imputed as a failure.
- **Tipping Point Analysis:** All discontinued primary eyes will be imputed as effectiveness failures. For primary eyes missing 12-month visit data for reasons other than discontinued, effectiveness will be initially be set to success. At this step, the lower limit of the one-sided 97.5% confidence intervals (CI) will be calculated. Serial calculations will then be performed using a decreasing number (i.e.,  $n-1$ ,  $n-2$ , ...1) of successes to determine the maximum number of additional failures allowed for the lower bound one-sided 97.5% CI of the effectiveness endpoint percent estimate to achieve or exceed 75% success.

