**TABLE 1: SCHEDULE OF VISITS AND MEASUREMENTS**

	Initial										Follow-up	
	Pre-Op	0 Day	1 Day	1 Week	1 Month	2 Months	3 Months	6 Months	12 Months	18 Months	24 Months	
Slit Lamp Biomicroscopy OD, OS	✓ 		✓	✓	✓	✓	✓	✓	✓	✓	✓	✓
Applanation Tonometry OD, OS	✓ 		✓	✓	✓	✓	✓	✓	✓	✓	✓	✓
Gonioscopy OD, OS	✓								✓			
Scleral Thickness Measurement OD, OS	✓											
Implant Assessment OD, OS			✓	✓	✓	✓	✓	✓	✓	✓	✓	✓
Axial Length / ACD OD, OS	✓								✓			✓
Corneal Topography / Keratometry OD, OS	✓											
Pupillometry OD, OS	✓ 	✓	✓	✓	✓	✓	✓	✓	✓	✓	✓	✓
Posterior Pole exam with 78 /90D lens OD, OS	✓ 		✓		✓	✓	✓	✓		✓		
Dilated Indirect Ophthalmoscopy 20/30D lens OD, OS	✓			✓					✓			✓
Visual Fields OD, OS	✓											
Cup/Disk Ratio OD, OS	✓								✓			✓
Cycloplegic Refraction w/ VA OD, OS	✓								✓			✓
Manifest Refraction OD, OS	✓			✓ 	✓	✓	✓	✓	✓	✓	✓	✓
BCDVA OD, OS	✓ 			✓	✓	✓	✓	✓	✓	✓	✓	✓
UCDVA OD, OS	✓		✓ 	✓	✓	✓	✓	✓	✓	✓	✓	✓
UCNVA @ 40 cm OD, OS, OU	✓						✓	✓	✓	✓	✓	✓
UCIVA @ 66 cm OU	✓						✓	✓	✓	✓	✓	✓
DCNVA @ 40 cm OD, OS, OU	✓				✓	✓	✓	✓	✓	✓	✓	✓
Patient Preferred Distance DCN - OD, OS, OU UCN - OU	✓						✓	✓	✓	✓	✓	✓
Minimum add to achieve 20/20	✓						✓ 					
NAVQ (Validated PRO) & Patient Questionnaire	✓							✓	✓	✓	✓	✓
Sub-Study Only Wavefront measurements 	✓						✓	✓	✓	✓	✓	✓
Sub-Study Only Defocus Curve 	✓						✓	✓	✓	✓	✓	✓

Visual acuity will be measured using pinhole on day 1

Fellow Eye Safety Exam (when fellow eye surgery is 61-180 days after primary eye surgery)

Randomized Sub-study subjects only – control group subjects are examined through 6 months and the surgery group through 24 months.

Measure BCDVA using baseline refraction

Examination methods are provided in Appendix 1: Examination Methods.

[REDACTED]

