#### Full Study Cohort Effectiveness Endpoint

The sample size calculation for the statistical hypotheses described for Objective #1 in Section 11.2 is based on the following criteria:

- The two-sided significance level = 0.05 (or one-sided significance level = 0.025).
- The statistical power = 90% at  $p = 0.825$ . The assumption of true responder rate of 0.825 is based on the simple average of success rate observed in previous Refocus clinical study data, as follows:
  - Disposable Scleratome group had an observed success rate of 88%.
  - Re-usable Scleratome group had an observed success rate of 77%.
  - Simple average of 88% and 77% is 82.5%.
- Binomial distribution is used for sample size calculation.

Based on the criteria above for Objective #1, 330 treated primary eyes should be available for analysis at 12 months. If a dropout rate of 10% of subjects by 12 months is considered, then the surgery cohort should include approximately 360 treated primary eyes.

For safety analysis, in order to detect an Adverse Event (AE) with a true probability of occurrence among subjects of 1% with 95% probability, based on the binomial distribution, a sample of at least 299 eyes would be required (in accordance with ANSI Z80 29 18Nov2013 AIOL [rev20]). Assuming a drop-out rate of approximately 10% of subjects by 12 months, the surgery cohort should include a minimum of 333 treated primary eyes.

A sample size of 333 treated primary eyes will meet the sample size requirements for both safety and effectiveness. The study cohort is planned for 360 surgery subjects at up to 14 study sites. However, no site may enroll and determine to be eligible more than 20% of the subject surgery cohort.

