**FIGURE 9 – ILLUSTRATION OF STUDY POPULATION AND ACCOUNTABILITY**

## 11.5 Subject Accountability

The following terms and definitions will be used for the accountability of the study population and are based on the definitions found in ANSI Z80.29 Rev 018, section B.5.3 as modified and explained below.

- Enrolled – the total number of subjects that have signed the full informed consent.
  - Enrolled but ineligible – the total number of subjects that have signed the full informed consent but do NOT meet all of the inclusion/exclusion criteria.
  - Enrolled and eligible – the total number of subjects that have signed the full informed consent and meet all of the inclusion/exclusion criteria.
- Surgical Withdrawal – Subjects (eyes) that have been enrolled and determined eligible but do not undergo surgical preparation of the ocular surface for any reason.
- Discontinued– Subjects (eyes) that have discontinued treatment prior to the visit window associated with the form as a result of death, the removal of all 4 implant segments (explant), or any other reason except lost to follow-up.
  - Explanted Eye – Eyes that underwent implantation surgery, but have had all implanted segments removed.
- Lost to Follow-up – Subjects that have withdrawn from the study after initial eye surgery or subjects that have missed the visit window associated with the form and all subsequent scheduled visits despite documented efforts by the Investigator to schedule the subject for follow-up.
- Missed Visit – Data for subjects (primary eyes) that is not available for a follow-up visit within the specified visit window associated with the form, but data is available for a subsequent follow-up visit for such subject.

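### The Objective #1 Worst Case Analysis carries forward the worst early value, so it is not a lower bound; its visit list also omits the scheduled 2-month visit

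*Combined protocol and SAP*

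**What the plan says.** The primary analysis of Objective #1 (Section 11.6) uses observed 12-month data, with explanted eyes as the only imputed failures. The criterion in Section 11.8 is exact: "This goal is met if the one-sided 97.5% lower confidence limit of the 12-month responder rate is at least 75" per cent.

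Section 11.8 then adds best case, worst case and tipping point analyses. Three rules make up the worst case:

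- Discontinued eyes are failures.
- For eyes lost to follow-up or without 12-month data, "the worst value from any protocol scheduled visit at 1 month or later (1 month, 3 month or 6 month visit) will be used".
- An eye with no such visit is a failure.

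Section 11.5 decides which eyes fall under which rule. Lost to follow-up includes "Subjects that have withdrawn from the study after initial eye surgery", and the definition of discontinued leaves out anyone lost to follow-up.

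Sections 7.2 and 8.5.1 schedule a 2-month visit. The Table 1 row "DCNVA @ 40 cm OD, OS, OU" is ticked at every visit from 1 month onward, including 2 months.

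**The concern.** A worst case is normally read as the least favourable result the missing data could produce. This rule does not give that. Suppose an eye met the endpoint at each listed visit it attended, even if that was only the 1-month visit, and was then lost. It enters the worst case as a 12-month success. The same holds for a subject who withdrew after surgery, because Section 11.5 keeps that subject out of the group that is failed automatically.

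The rule also contradicts itself. Its general phrase covers every scheduled visit from 1 month on, while the parenthesis names only 1, 3 and 6 months. Two programmers could produce different figures from the same data.

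What is at stake is the figure labelled worst case in the report: it can be at or above 75% when the actual worst case is below it.

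**Working it through.** **Inputs.** Section 11.3 gives a one-sided level of 0.025, an assumed true rate of 82.5%, and dropout of 10% from about 360 treated primary eyes. Section 11.8 gives the goal of 75% and the exact binomial limit. The one-sided 97.5% lower limit for x successes in n eyes is L(x, n), the 0.025 quantile of a Beta(x, n − x + 1) distribution.

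**The plan's own figure.** Section 11.3 states that "330 treated primary eyes should be available for analysis at 12 months" for 90% power. At n = 330 the smallest passing count is 264 (80.0%): L(264, 330) = 75.27% and L(263, 330) = 74.95%. Exact power at a true rate of 0.825 is 0.896, with exact one-sided alpha 0.0192. The stated design is reproduced to within rounding.

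**Passing count with all treated eyes in the denominator.** L(287, 360) = 75.19% and L(286, 360) = 74.90%, so 287 of 360 (79.7%) are needed.

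**Illustration.** Missing eyes: 0.10 × 360 = 36, all assumed not discontinued. Observed eyes: 360 − 36 = 324. Take 267 responders, 267/324 = 82.4%, close to the design rate.

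| Treatment of the 36 missing eyes | Successes / eyes | Lower limit | 75% goal |
|---|---|---|---|
| Left out (primary analysis) | 267/324 | 77.8% | met |
| All failures (actual worst case) | 267/360 | 69.3% | not met |
| Plan's rule, 11 carried as success | 278/360 | 72.5% | not met |
| Plan's rule, 18 carried | 285/360 | 74.6% | not met |
| Plan's rule, 20 carried | 287/360 | 75.2% | met |
| Plan's rule, 25 carried | 292/360 | 76.7% | met |

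The switch comes at 287 − 267 = 20 carried successes, 20/36 = 56%. The counts 11, 18 and 25 stand for roughly 30%, 50% and 70% of 36. These shares are assumptions, since the documents give no 1-month responder rate from which to estimate them.

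**With 30 missing (360 − 330).** 272/330 observed (82.4%) becomes 272/360 with all missing eyes failed, lower limit 70.8%, not met. The plan's rule passes from 287 − 272 = 15 of 30 carried.

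**What the tipping point analysis shows on the same data.** It starts with all 36 as successes: 267 + 36 = 303. The number of failures tolerated is 303 − 287 = 16 of 36.

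**How often an all-failure analysis would pass.** At a true rate of 0.825 with no discontinued eyes, the probability of at least 287 responders among those observed is 0.017 with 30 missing and 0.002 with 36 missing. The observed rate would have to reach 287/330 = 87.0% or 287/324 = 88.6%.

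**The 2-month visit.** For an eye with at least one other listed visit, leaving out 2 months can only keep its worst value the same or make it better. For an eye whose only visit from 1 month on is at 2 months, the list makes it a failure, while including that visit could make it a success. The effect is therefore small and not in one direction.

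**The case against.** The strongest answer is the tipping point analysis in the same section. In the illustration it reports that 16 of 36 failures are tolerable, which tells a reader that all-failure would not pass. Its printed sequence ends at 1 success, but the tolerated maximum still carries the message. A reader might infer that the mislabelled figure would support a false claim of robustness. With this analysis reported beside it, the documents do not support going that far. What remains is that the tipping point does not turn a separately reported worst case into a floor.

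A reader might also infer that early success tends to fade, citing the loss of near vision in Section 6.2. That section ties the loss to displaced segments of the earlier model and says the redesign holds the segment in place. For the redesigned model, Section 6.3 reports DCNVA of 20/40 or better at 80% (237/298), 84% (210/249) and 91% (120/132) at 12, 18 and 24 months, though with shrinking denominators and without the 10-letter condition. Section 11.3 says the earlier 6-month responder rate was below the 12-month rate. Early values may therefore be conservative on average. This stands, but a bound concerns the unfavourable possibility, not the average.

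Nor do the documents say why subjects withdraw, so treating withdrawals as dissatisfied subjects is inference. Eyes with all segments removed are failed in any case.

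Finally, an all-failure rule is harsh. It fails missed-visit eyes, which by definition have later data, and it would seldom pass at the planned rates. That is a good reason to keep the present rule as a second analysis under an accurate name.

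**Conclusion.** The point holds as one about a mislabelled sensitivity bound and a visit list that contradicts its own general phrase. Under the stated assumptions (360 eyes, 36 missing, none discontinued, 267/324 observed), the actual worst case has a lower limit of 69.3%, while the plan's version meets the 75% goal from 20 carried successes upward. Whether 20 of 36 would be carried cannot be judged from the documents. A carried success needs every available listed visit to meet both the 20/40 and the 10-letter conditions, and any discontinued eyes among the 36 would lower the number that could be carried.

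A reader might take this as a threat to the Objective #1 conclusion. It is not: the primary decision rule, its handling of missing data and the sample size do not depend on this analysis.

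**What to change.** In Section 11.8:

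1. Define the Worst Case Analysis as every primary eye without 12-month data imputed as failure, whether withdrawn, lost or missing only that visit. Extending the tipping point sequence to 0 successes gives the same figure.
2. Keep the present rule, renamed as a worst-observed-value analysis.
3. List 1, 2, 3 and 6 months in both the best- and worst-value rules, so that the list agrees with Table 1 and the general phrase.

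The cost is a wording change and one extra line of output, with no new data. The downside is a less favourable worst-case figure that will usually fall below 75% at the planned response and dropout rates. It should therefore be presented next to the tipping point result.

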### **Sensitivity Analysis of Objective #2:**

- **Tipping Point Analysis:** All discontinued primary eyes will be iteratively imputed as effectiveness success or failures. Let  $n_1$  and  $n_2$  be the number of discontinued primary eyes for the randomized surgery group and the randomized control group, respectively. For the  $n_1$  discontinued randomized surgery group primary eyes, they can be imputed as 0 failures, 1 failure, 2 failures, and up to  $n_1$  failures, for a total of  $(n_1+1)$  possible imputations. For the  $n_2$  discontinued randomized control group primary eyes, there are  $(n_2+1)$  possible imputations. Therefore, there are  $(n_1+1) \times (n_2+1)$  possible combinations of success and failure imputations for these discontinued

primary eyes. For each of these possible imputations, the lower limit of the one-sided 97.5% confidence intervals (CI) will be calculated. The imputations that have the lower one-sided 97.5% CI < 75% will be identified.

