#### Objective #2:

An analysis of the randomized surgery group and randomized control group will be conducted. The randomized surgery group is defined as successful if the percentage of primary eyes achieving the effectiveness endpoint at 6 months postoperative (6-month responder rate) is higher than the percentage in the randomized control group. The corresponding null and alternative hypotheses are as follows:

$H_0$  (null hypothesis):  $p_1 \leq p_2$

$H_a$  (alternative hypothesis):  $p_1 > p_2$

Where:

- $p_1$  is the percentage of primary eyes in the randomized surgery group who achieve the effectiveness endpoint at 6 months.
- $p_2$  is the percentage of primary eyes in the randomized control group who achieve the effectiveness endpoint at 6 months.

The primary eye is defined as the subject's dominant eye and the eye that will undergo surgery first. It is intended that all subjects will also undergo surgery in the fellow eye at a subsequent date as specified in the protocol.

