## 11.6 Analysis of Effectiveness Cohorts

For the primary analysis of Objective #1, all observed 12-month data of the surgical primary eyes will be included in the effectiveness analysis. Missing data will not be imputed except that explanted primary eyes will be imputed as failures.

For the primary analysis of Objective #2, all reported 6-month data of the randomized primary eyes will be included in the analysis. Missing data will be imputed as follows:

- Randomized Control Group: In the absence of 6 month visit data, the nearest available data recorded between and including the 3 month visit up to the 6 month visit will be utilized. Since this randomized control group does not receive the benefit of the surgery during this 6 month observation period, the lost to follow-up and missed visit rate could be higher and since no intervention occurs during the 6 month period, this imputation of missing data is warranted. In the absence of any observed data between the 3 month visit

and 6 month visit, this missing data will not be imputed since failure to achieve the effectiveness endpoint is expected.

- Randomized Surgery Group:
  - Explanted primary eyes will be imputed as failures.
  - In the absence of 6 month visit data, the nearest recorded data after 6 months up to and including 12-month visit data will be used. This imputation is warranted as the visit data between 6 and 12 months provides a predictive indicator of 6 month results. In the absence of any observed data between 6 and including 12 months, this other missing data will not be imputed.

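### The Objective #2 tipping-point analysis is judged against the 75% goal of Objective #1, not against surgery being better than control, and it varies the wrong set of eyes

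*Combined protocol and SAP*

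**What the plan says.** Section 11.2 defines success on Objective #2 as a 6-month responder rate in the randomized surgery group that "is higher than the percentage in the randomized control group". Section 11.8 gives the test: the two-sided Fisher's "exact test will be used to compare the difference between 6-month responder rates of the two randomized groups".

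The 75% figure belongs to Objective #1. Section 11.8 says of that objective: "This goal is met if the one-sided 97.5% lower confidence limit of the 12-month responder rate is at least 75" percent. Its tipping-point analysis accordingly looks for the number of failures that still allows the lower limit of the one-sided "97.5% CI of the effectiveness endpoint percent estimate to achieve or exceed 75% success".

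For Objective #2, the tipping-point paragraph begins "All discontinued primary eyes will be iteratively imputed as effectiveness success or failures". It builds a grid of (n1+1) × (n2+1) combinations from the discontinued eyes of the two arms, calculates a one-sided 97.5% lower limit for each, and ends: "The imputations that have the lower one-sided 97.5% CI < 75% will be identified".

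Section 11.5 defines discontinued eyes as those that stopped because of death, explant, "or any other reason except lost to follow-up". Section 11.6 says for Objective #1 that "explanted primary eyes will be imputed as failures", and repeats that rule for the randomized surgery group under Objective #2. It fills other missing 6-month values from neighbouring visits where it can, and leaves the rest unimputed.

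**The concern.** A tipping-point analysis should show which assumptions about missing outcomes would reverse the conclusion of the test it supports. Here that conclusion is that surgery beats control. A 75% floor on a lower confidence limit is a different question, carried over from the other objective.

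The paragraph also does not say what the limit is a limit of. If it is the surgery rate, the n2+1 control imputations cannot change any result, so half of the grid does nothing. If it is the difference p1 − p2, 75% has no stated basis, it exceeds the planned difference, and no interval method is named.

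The eye set has two narrower faults. Explanted eyes fall within the discontinued category, so they may be set to success although Section 11.6 fixes them as failures. Eyes lost to follow-up are outside that category, so those with no outcome after the Section 11.6 rules are never varied. The Objective #1 tipping point does the opposite: it fixes discontinued eyes as failures and varies the other missing eyes.

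Study success needs both objectives, and Objective #1 has best-case, worst-case and tipping-point analyses while Objective #2 has only this one. Run literally, it could make a robust result look fragile. A correction made after the data are seen would be post hoc.

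**Working it through.** **Inputs from Section 11.3.** Surgery rate 0.75 and control rate 0.10 at 6 months; 30 per arm; 10% dropout; two-sided alpha 0.05. The 12-month rates 0.825 and 0.88 from the same section serve only as an upper range. The responder counts below are assumed.

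**1. The plan's own figure.** Summing over all binomial tables at 0.75 against 0.10, Fisher's exact test with 14 per arm has power 0.934, one-sided 0.025 or two-sided 0.05. The stated power above 90% is reproduced. At 30 per arm the power is 0.9998.

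**2. When can the limit reach 75%?** The exact one-sided 97.5% lower limit for x of n is the 0.025 quantile of Beta(x, n − x + 1).

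- 27/30: 73.5%; 28/30: 77.9%
- 24/27: 70.8%; 25/27: 75.7%

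So 28 of 30, or 25 of 27, responders are needed. The probability that a single result falls below 75% is:

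| True surgery rate | n = 27 | n = 30 |
|---|---|---|
| 0.75 | 97.9% | 98.9% |
| 0.825 | 87.5% | 91.6% |
| 0.88 | 64.5% | 71.5% |

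At the planned rate the rule is therefore almost always triggered, even with no missing data.

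**3. Worked grids.** Take 27 observed and 3 missing eyes per arm (30 × 10% = 3), which gives (3+1) × (3+1) = 16 combinations with denominators of 30.

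| | 20/27 vs 3/27 | 24/27 vs 3/27 |
|---|---|---|
| Exact limit, surgery rate | 47.2% to 57.7% | 61.4% to 73.5% |
| Newcombe limit, p1 − p2 | 21.8% to 43.1% | 35.5% to 57.9% |
| Wald limit, p1 − p2 | 24.5% to 48.1% | 39.8% to 64.8% |
| Identified by the 75% rule | 16 of 16 | 16 of 16 |
| Largest Fisher p | 0.00057 (20/30 vs 6/30) | 6.3 × 10⁻⁶ (24/30 vs 6/30) |
| Fisher p > 0.05 | 0 of 16 | 0 of 16 |

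Both readings of the limit identify everything, and nothing overturns the test.

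**4. The difference reading.** The planned difference is 0.75 − 0.10 = 0.65, already below 0.75. At the extreme the answer depends on the unnamed method: 30/30 against 3/30 gives 70.7% by Newcombe and 79.3% by Wald.

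**5. Over repeated sub-studies.** Let each eye be missing at random with probability 0.10, and read the limit on the surgery rate. Every imputation is identified when even the most favourable one, with all missing surgery eyes set to success, has at most 27/30. Each eye then counts as a success with probability 0.10 + 0.90p: 0.775, 0.8425 and 0.892 for the three rates. The binomial probability of at most 27 of 30 is about 98%, 87% and 64%. In 20,000 simulated sub-studies per rate, with a control rate of 0.10, Fisher's test stayed significant under the most adverse imputation in 96%, 99% and 99.8%.

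**6. Eye set.** An explanted surgery eye is fixed as a failure in Section 11.6, but the grid includes combinations in which it is a success. A surgery eye lost to follow-up with nothing recorded from 6 through 12 months has no outcome under Section 11.6 and is not in n1. A control eye lost before the 3-month visit is in the same position for n2.

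**The case against.** The strongest reply is that little depends on this. The analysis is supportive, no success rule uses it, and the simulation itself shows that Fisher's test is very hard to overturn. The correct grid could be rebuilt from the final counts. That stands, and it limits the weight of the point. It does not make the rule right: a robust result is exactly what the analysis should be able to show, and this one would show the reverse.

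On explants, the grid always includes the case in which all of them fail. Allowing successes adds favourable combinations and hides no adverse one. That is fair, but it still conflicts with Section 11.6.

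On loss to follow-up, the gap is narrow. Section 11.6 fills many missing visits. A control subject who actively withdraws has had no surgery and may count as discontinued, and so be varied. What remains is mainly surgery eyes with nothing from 6 through 12 months and controls lost before 3 months.

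The worked grids vary all of the dropout, although the written rule would vary only the discontinued part. The threshold result does not depend on this: with no eyes varied, 20/27 and 24/27 are both below the 25/27 needed to reach 75%. The grids do not measure the effect of the eye-set faults.

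Finally, the effectiveness cohort leaves out randomized surgery subjects who never receive an implant segment. The fix below follows the plan's own cohort and does not settle that separate question.

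**Conclusion.** The concern holds. The Objective #2 tipping-point rule is wrong as written, because its 75% criterion belongs to Objective #1 and neither reading of the limit makes it informative about p1 > p2. Near the planned rates it would identify every imputation in about 98% of sub-studies, while the Fisher conclusion would survive the most adverse imputation in about 96%. If the true surgery rate were as high as 0.88, the first figure would still be about 64%. These figures assume 30 per arm, a 10% control rate, 10% missing at random per arm and the limit read on the surgery rate.

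The two eye-set faults are confirmed from the definitions but are smaller and not quantified. The primary Fisher test, its error rate and the sample size are unaffected. The text should be corrected before the data are analysed.

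**What to change.** In the Objective #2 tipping-point paragraph of Section 11.8:

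- Replace the last two sentences with: For each of the (n1+1) × (n2+1) combinations, the two-sided Fisher's exact test will be repeated. Combinations with p > 0.05, or with a surgery responder rate not higher than the control rate, will be identified.
- Define n1 and n2 as the effectiveness-cohort primary eyes in each randomized group that still have no 6-month outcome after the Section 11.6 rules: lost to follow-up, discontinued for a reason other than explant, or any remaining missed visit.
- Keep explanted eyes as failures, as Section 11.6 states.
- Do not offer a confidence-limit rule as equivalent. With 8/30 against 2/30, Fisher p = 0.080, but the lower limit for p1 − p2 is above zero by Newcombe (+0.007) and Wald (+0.018), so the two rules can disagree.

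The cost is three or four sentences, with no new data, visits or subjects.
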